We designed the present randomized trial to test whether 12 weeks of supervised weekly Kundalini yoga class and a brief daily home meditation practice can improve cognitive function among older women with high AD risk compared to weekly classes of memory training with daily homework. Our choice of interventions is based on prior studies of mind-body exercise in older adults that revealed robust cognitive benefit, as well as our own studies of this intervention compared to cognitive memory training in older adults with MCI. Kundalini yoga has also been observed to impact the frontal lobes, likely due to increased cerebral blood flow ([name] et al., 2013b).

The primary outcome will be memory performance at 12 weeks (i.e., immediately post-treatment).

Secondary outcomes include measures of executive functioning and changes in brain structure and connectivity.

Specific Aim 1: To evaluate effects of Kundalini Yoga+ Kirtan Kriya (KK+KY) and Memory Enhancement Training (MET) on memory performance in women with high AD risk.

Hypothesis 1: Improved memory performance will be observed in women receiving KK+KY and MET at 12 weeks compared to baseline.

Specific Aim 2: To test the efficacy of KK+KY vs. MET for improving executive functioning including working memory.

Hypothesis 2: KK+KY will improve performance in executive functioning to a greater extent than MET.

Exploratory Aim 3a: To test the effects of MET vs. KK+KY on structural and functional connectivity and task-related activation for working and episodic memory.

Hypothesis 3a: Compared to MET, KK+KY will be associated with greater improvement in connectivity in regions associated with working and episodic memory.

Exploratory Aim 3b: To test the effects of MET vs. KK+KY on levels of cellular and genomic markers of inflammation, telomerase activity level, and telomere length after 12 weeks and at 6 and 12 month follow-up.

Hypothesis 3b: Compared to MET, KK+KY will be associated with decreases in cellular and genomic markers of inflammation and increases in telomerase activity level and telomere length after 12 weeks and at 6 and 12 month follow-up.

Exploratory Aim 3c: To explore whether KK+KY results in reduced cardiovascular risk factors compared to MET, and whether this effect will correlate temporally with changes in fMRI measures and clinical outcomes.

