outcome will be an average of the participant's z-scores on three tests. Two of these tests will be of verbal memory tests: 1) the Hopkins Verbal Learning Test (HVLT) (total and delayed recall scores) (Shapiro et al., 1999), and (2) the Wechsler Memory Scale (WMS-IV) (immediate and delayed) and one will be of visual memory (the Rey-Osterreith Complex Figure 3-minute delay recall). The secondary outcome measure of executive functioning will include Trail Making B and Stroop Color-Word Interference tests to estimate mental flexibility and inhibition/adjustment of behavior. Tests of language fluency will include Animal fluency and CFL Letter Fluency to assess strategic searching/organization of verbal knowledge, as well as the Boston Naming Test. The battery will also include measures of attention/ processing speed which are commonly impaired in the geriatric population according to prior research by our group (Schneider, [name], Siddarth, & [name], 2012) and others (Alexopoulos, Kiosses, Klimstra, Kalavam, & Bruce, 2002; Bhalla et al., 2009; Butters, 2004; Favrod et al., 2015; Lockwood, Alexopoulos, & van Gorp, 2002). These tests place significant demand on mental operations that require speed, manipulation and monitoring of information that is in conscious awareness (Trail Making A; Digit Span; Stroop Color and Word). Most of the measures have 2 or 4 alternate forms so that unique forms may be administered to participants during repeat testing. We include both traditional, standardized tests and computerized tests for enhanced sensitivity of the battery to potential intervention effects and so that our results can also be compared with other findings in the literature. In addition to the cognitive outcome measures, we will include the TOPF to estimate pre-morbid cognitive functioning.

Secondary clinical outcome measures will include the Clinical Global Impression- Severity and Improvement scale (CGI)(Busner, Targum, & Miller, 2009) to quantify overall severity and clinical improvement over time (2 min). Subjective memory complaints will be assessed via the 10-item Memory Functioning Questionnaire scale. The Beck Depression Inventory (BDI) (Beck, Steer, & Brown, 1996; Beck, Steer, & Carbin, 1988), a self-assessment scale of depression (5 min), will also be administered, as will the Hamilton Anxiety scale.

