Data will be analyzed using the SAS (v9.4) statistical package. Data will be examined initially to identify issues such as departures from normality, which might suggest the need for transformation (e.g., logarithmic). Demographic variables (e.g., age, gender, etc.) will be compared by treatment group and examined in relation to outcome variables; this would define one possible set of appropriate covariates, if needed. Correlations (a) among outcome measures and (b) among potential covariates will be examined to eliminate redundancy via possible data reduction, e.g., formation of composite scores or selection of single measures from sets of highly inter-correlated variables. Cognitive domain scores will be obtained as follows: for each neuropsychological test, raw scores will be converted to standardized (Z) scores with a mean of 0 and a SD of 1, based on all participants combined. Then, for each of the tests in a cognitive domain, the Z scores will be averaged to create a single Z score per cognitive domain.

The independent samples *t*-test or Chi-square test will be used to compare the demographic characteristics between the MET and KK+KY control group. The effect of intervention over time on the cognitive functions will be investigated in intention-to-treat (ITT) analyses. Measurements will be analyzed using linear mixed models; analyses will assume missing at random with missingness allowed. All models will include random intercepts to account for correlations between the repeated measures for each participant. The fixed components of the models will include effects of group and time and a group X time interaction, with post hoc analyses between times and groups. All statistical significance tests will be two-sided, and an alpha-level of 0.05 will be considered statistically significant for primary analyses and Bonferroni correction will be employed for post hoc analyses.

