Power analysis: The power analysis is focused on the primary aim of the study to assess whether the KK+KY and MET groups demonstrate comparable improvement in memory performance. We plan to enroll a total of 100 women in the study, anticipating an attrition rate of at most 10% based on our previous studies. Thus, we will most likely have a total of 90 completers. With a sample size of 45 per group, we achieve 80% power to detect equivalence within a margin of equivalence of 0.62, when the true difference between the means is assumed to be zero. In the PI's previous study using similar interventions on older adults with MCI, a between-group effect size of 0.3-0.4 was observed for the memory measures. In the proposed study, the target population is women with high risk for AD, hence we believe that the proposed sample size will have sufficient power to address the primary hypothesis of the study. With this sample size, we can also expect to detect an effect size of 0.60 at a significance level of 0.05 and 80% power for the secondary outcome measure (executive functioning). We intend to test the secondary outcomes adjusting for multiple comparisons using the Benjamini-Hochberg false discovery rate approach (which is more powerful than the simple Bonferroni correction). Further, we will report results of all proposed analyses and conclusions will be based on the pattern of results.

Data management: Data management and analysis support will be provided by the UCLA Semel Institute Statistical Core (SI-Stat) ([name]). The SI-Stat will provide needed software and technical support with a data manager operating under the supervision of [name]. The SI-Stat has a Dell PC computer network with

automated CD R/W backup and is set up for medium to large-scale data processing and analysis using available commercial database and statistical software. **1. Randomization.** Randomization schedules will be prepared in a masked manner by the statistician. **2. Data submission and quality control.** Data forms will be delivered from the originating location to the central data unit within one week of being generated. When errors, omissions, or unclear information is detected on the paper forms, a copy will be returned for corrections. The data manager will generate monthly reports summarizing missing and incorrect data will be sent to the PI.

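### The 80% power quoted for executive functioning uses an unadjusted 0.05, but the plan tests the secondary outcomes with Benjamini-Hochberg, so for the significance level it is an upper bound

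*Combined protocol and SAP*

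**What the plan says.** Power analysis: the calculation is made "With a sample size of 45 per group", and for executive functioning "we can also expect to detect an effect size of 0.60 at a significance level of 0.05 and 80% power". The sentence after it reads "We intend to test the secondary outcomes adjusting for multiple comparisons using the Benjamini-Hochberg false discovery rate approach". No family size and no power at an adjusted level are given.

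Data analysis: "All statistical significance tests will be two-sided". The 0.05 level is assigned there to primary analyses, and each cognitive domain is reduced to one averaged Z score.

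Secondary outcomes: the list just before the Specific Aims says that they "include measures of executive functioning and changes in brain structure and connectivity"; the abstract names the same three items. Further on, Exploratory Aim 3a covers structural and functional connectivity, so connectivity is labelled both secondary and exploratory. The outcome measures section has a further paragraph on "Secondary clinical outcome measures" (CGI, the Memory Functioning Questionnaire, BDI and Hamilton Anxiety), without saying whether these belong to the adjusted family.

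Hypothesis 2 predicts that KK+KY improves executive functioning more than MET.

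**The concern.** The power statement and the test it describes use different thresholds. The effect size is powered at 0.05, whereas the planned procedure compares the ordered p-values with fractions of 0.05 that depend on how many outcomes are in the family and how many of them are rejected. Averaging Trails B and Stroop into one domain score leaves executive functioning with a single test, but it does not lift the adjustment while other outcomes share the family.

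Hypothesis 2 is the only non-exploratory numbered hypothesis that predicts superiority of KK+KY. A null result there would be read against a claimed 80% chance of detecting 0.60 SD. Because the family is not listed, its membership could also be settled after the data are seen, and that choice changes the power.

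**Working it through.** **Inputs.** From Power analysis: 45 completers per group, effect 0.60 (standardised, so SD = 1), level 0.05, target power 80%. From Data analysis: two-sided tests. From the randomisation section: 1:1 allocation. The family size m is not in the documents and is assumed below.

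**Step 1: reproduce the stated figure.** Two-sample t-test with 2 × 45 − 2 = 88 degrees of freedom. Noncentrality = 0.60 × √(45/2) = 2.846. The two-sided 0.05 critical value is 1.987. Power = P(T₈₈(2.846) > 1.987) = 80.4%, and the effect detectable with 80% power is 0.597. The normal approximation gives 81.2%. One-sided 0.05 gives 88.1% and two-sided 0.025 gives 71.4%. The plan's figure is thus the unadjusted two-sided 0.05 one, and it is correct for those inputs.

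**Step 2: the Benjamini-Hochberg threshold.** Order the m p-values. The procedure finds the largest i with p₍ᵢ₎ ≤ 0.05 × i/m and rejects the i smallest. The threshold that applies to executive functioning is therefore 0.05 × (number rejected)/m. It equals 0.05 only if all m are rejected, and it is 0.05/m if executive functioning is rejected alone.

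**Step 3: the strictest step, 0.05/m** (same t formula, 45 per group).

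| m | 0.05/m | Power at 0.60 SD | Effect detectable at 80% |
|---|---|---|---|
| 1 | 0.0500 | 80.4% | 0.60 SD |
| 2 | 0.0250 | 71.4% | 0.66 SD |
| 3 | 0.0167 | 65.7% | 0.69 SD |
| 7 | 0.0071 | 53.9% | 0.76 SD |

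Here m = 3 counts executive functioning, brain structure and connectivity as one test each; m = 7 adds the four clinical scales named above.

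**Step 4: the full procedure.** The strictest step is only the floor, so the whole procedure was simulated (200,000 replicates, t-tests with 88 degrees of freedom, true effects of 0.60 SD, correlation between outcomes of 0 or 0.5). Power for executive functioning:

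- m = 3: 66–67% if it is the only true effect, 72–73% with two true effects, 77–78% with three.
- m = 7: 54–55% if it is the only true effect, 75–77% if all seven are true.

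No scenario with m > 1 reached 80%.

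**The case against.** **The family could be a single test.** Power analysis speaks of "80% power for the secondary outcome measure (executive functioning" in the singular, the analysis paragraph for the primary outcome names only executive function as secondary, and connectivity also sits under an exploratory aim. With m = 1 nothing is lost. This reading stands as a possibility, but the plural in the adjustment sentence, the two lists of secondary outcomes and the fact that one test needs no adjustment all weigh against it.

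**The loss may be small.** The protocol expects benefit in other outcomes too. If all members of the family truly respond, the loss is only about 2 to 5 points. This stands, and it is why the floor alone would mislead.

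**Family membership is not documented.** A reader might infer that the clinical scales are under the same false-discovery-rate control. No sentence says so, and further scales follow them in the outcome section. Nor are brain structure and connectivity single tests in the imaging plan. So m = 3 and m = 7 are illustrations.

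**Other features move power as well.** The plan uses intention-to-treat mixed models; 50 per group would give 84.4% at 0.05. The 35–36 completers per group expected at 12 months would give 70–71%. The 80% is thus an upper bound for the significance level only, and not a best case in general.

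**The figure is ancillary.** The power section is directed at the primary aim, and this is a secondary outcome. That limits the weight of the point but does not remove the mismatch.

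**Conclusion.** The point holds as a mismatch between the quoted power and the planned test. The 80% at 0.60 SD belongs to an unadjusted two-sided 0.05; under Benjamini-Hochberg with more than one test, the planned procedure delivers less. The size depends on an unstated family. Assuming three tests, power is about 66% (only true effect), 73% (two true effects) or 78% (three); assuming seven, about 55% to 77%. These figures rest on 45 per group, a two-sample comparison, and true effects of 0.60 SD wherever an effect is assumed.

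Two stronger readings are not supported. One is that the 80% was miscalculated: it is right for its stated inputs. The other is that executive functioning is the only outcome where KK+KY is expected to do better: Hypotheses 3a and 3b also predict superiority, as exploratory hypotheses, and the text expects it for impulsivity too. What sets Hypothesis 2 apart is that it is the only non-exploratory numbered one.

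**What to change.** Preferred: name the executive-function composite as the single key secondary endpoint, tested at two-sided 0.05, and place imaging and the clinical scales in a separate Benjamini-Hochberg family. The stated 80% is then correct as it stands, and the double labelling of connectivity is settled at the same time.

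Otherwise: list the members of the Benjamini-Hochberg family and restate power at 0.60 SD, or the detectable effect, as a range from the 0.05/m threshold to 0.05. If the family were three tests, this would read 66% to 80% power, or 0.69 to 0.60 SD detectable with 80% power. The numbers must follow from the family that the sponsor names.

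Cost: wording only, with no change to sample size, visits or interventions. The downside is that imaging leaves the executive-function family, or that the quoted figure becomes less favourable.

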We propose a randomized controlled design for this pilot 12-week trial of the behavioral intervention MET compared to KK+KY for improving cognitive performance and health in women at high risk of AD. We hope to control for nonspecific factors by using a gold standard active control condition that has demonstrated acceptability in this population.

The proposed study will to test whether KK+KY is superior to MET for improving cognitive functioning, health (including cardiovascular factors), and mood in women with high AD risk. All participants will be recruited from the UCLA Women's Cardiovascular Center, UCLA outpatient clinics and the UCLA Longevity Center Program. All participants will be identified as having high AD risk including subjective memory complaints and high cardiovascular risk based on the 2013 ACC/AHA Guideline on the Assessment of Cardiovascular Risk (Goff et al., 2014). Follow up of all enrolled subjects at 6- and 12-months (52 weeks total) will allow detection of any continued cognitive or health benefits.

b) Methods for reducing risk of bias:

Participants will be informed prior to enrollment that they will receive one of two evidence-based interventions for improving memory. Descriptions of the study will be designed to minimize risk of possible between group differences resulting from differences in treatment expectancy. Differences in treatment expectancy/ credibility will be tested for at baseline, week 12, and week 24 as specified below. We will also control for the "instructor" effect if several instructors teach classes. The feasibility of weekly yoga/MET classes and homework time was assessed during previous studies and found reasonable for participants to complete (Eyre et al., 2016; H. Yang et al., 2016). Behavioral raters will be blind to group assignment.

1. Study Population: We anticipate screening about 250 subjects to recruit 100 women with subjective memory complaints and high cardiovascular risk based on the 2013 ACC/AHA Guideline on the Assessment of Cardiovascular Risk. Participants will be recruited from the women's clinics and geriatric clinics at UCLA as well as the UCLA Longevity Center.

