Each of these methods has significantly contributed to ongoing recruitment for other studies in our laboratory. [name] also has links to the local community of care providers for the elderly and to mental health professionals who could serve as a source of referrals. We anticipate having no competition with other studies for the same study population (i.e., those 50 years and older).

Recruitment. Participants will be recruited, assessed and randomized according to the scientific protocol and the consent procedures approved by the UCLA Institutional Review Board and the Office of Protection of Research Subjects. We project a recruitment period of two years to achieve recruitment of 100 participants. Our current rate of recruitment into antidepressant clinical trials for participants 55 years or older averages about 4-5 participants/month. We anticipate that the incentive to participate will be sufficient since participation includes free MET and KK-KY classes. Data analysis will be performed in year 2. We anticipate the dropout to be about 10% (45 completers per group) in the first 12 weeks, and additional 10% at 6 months and 12 months, leading to 35-36 completers per group at 12 months.

Table 6. Timeline.

Years of the project	Activities
Year 1,	Review assessment instruments; Inter-rater reliability sessions. Develop patient schedule with
	25

Years of the project	Activities
months 1-4	the UCLA CRC. Develop patient database with [name] and research assistants. Start subject recruitment at month 4.
Year 1, months 4-12	Continue recruitment (50 participants).
Year 2	Continue recruitment (50 participants). Conduct inter-rater reliability sessions.

Retention of participants. We have developed several successful strategies for retention of elderly participants. These include an ongoing and continuous process of consent to study procedures, involvement of family members whenever possible, and use of concerned and empathic clinicians and staff. However, it is important to note that our data analytic approach is robust to attrition.

Cohort maintenance. The comprehensive evaluation of participants prior to randomization and entry into the treatment trial is designed to minimize attrition. The evaluation of weekly compliance questionnaires will also alert the PI to potential attrition problems.

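### The stated timeline does not fit together: recruitment runs through year 2 and analysis is placed in year 2, but every woman is to be followed for 12 months

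*Combined protocol and SAP*

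**What the plan says.** All of this is in the Combined protocol and SAP.

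- **Recruitment (Human Subjects).** "We project a recruitment period of two years to achieve recruitment of 100 participants". A few sentences later: "Data analysis will be performed in year 2". No month is given, and nothing says whether the analysis is primary, interim or final. The next sentence projects 45 completers per group at 12 weeks and 35-36 per group at 12 months.
- **Table 6, Timeline.** Under year 1: "Start subject recruitment at month 4". Both the months 4-12 row and the year 2 row read "Continue recruitment (50 participants" each. The table ends with year 2 and shows neither a follow-up period nor an analysis period.
- **Introduction, outcomes and aims.** The primary outcome "will be memory performance at 12 weeks (i.e., immediately post-treatment".
- **Study Design, a).** "Follow up of all enrolled subjects at 6- and 12-months (52 weeks total) will allow detection of any continued cognitive or health benefits". Table 4 and the Study intervention procedures section put the last visit at 48 weeks instead.
- **Data analysis, Primary outcome.** The mixed model compares the groups at 12 weeks, 6 months and 12 months.
- **Power analysis.** 45 women per group give 80% power for equivalence within a margin of 0.62, with a true difference of zero.

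**The concern.** A woman who enters at the end of year 2 has her week-12 visit about three months into a third year and her last visit near the end of it. The plan names no third year, no data cut-off and no event that triggers an analysis. The only sentence that dates the analysis puts it before much of the promised follow-up can have taken place.

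What is at stake is durability first. Effects at 6 and 12 months are part of the primary model and of Hypothesis 3b, and year-2 recruits could contribute almost nothing at 12 months. Next is the primary endpoint: a literal reading could leave some women without week-12 data. Last, with no trigger written down, the date of the first between-arm comparison is left to later choice.

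**Working it through.** **Inputs.** Accrual of 50 women in months 4-12 and 50 in year 2 (Table 6); visits at weeks 12, 24 and 48 (Table 4) or 52 (Study Design, a); dropout of 10% to week 12 (Recruitment); margin 0.62 and 45 per group (Power analysis).

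**Assumptions not in the documents.** Even accrual within year 2, a cut-off at the last day of month 24, no delay between enrolment and first class, and a margin in SD units.

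**1. The plan's own figures reproduce.**
- Total: 50 + 50 = 100, and 100/24 = 4.2 per month.
- Week-12 completers: 50 × 0.9 = 45 per group.
- 12-month completers: 50 − 5 − 5 − 5 = 35, or 50 × 0.9³ = 36.5, matching 35-36.
- Power, two one-sided 5% tests, normal approximation: 2Φ(0.62/√(2/45) − 1.645) − 1 = 2Φ(1.296) − 1 = 0.805. With t tests it is 79.7%.

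**2. Women who cannot have reached each visit by month 24.** Year-2 accrual is 50/12 = 4.17 per month, and one month is 4.348 weeks. The number short is 4.17 × (visit time in months).

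| Visit | Months after entry | Women short, of 100 |
|---|---|---|
| Week 12 | 2.76 | 11.5 |
| Week 24 | 5.52 | 23.0 |
| Week 48 | 11.04 | 46.0 |
| Week 52 / 12 months | 12 | 50 |

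**3. Conditional effect on the primary comparison.** (100 − 11.5) × 0.9 = 79.7 women with week-12 data, about 40 per group. Power: 2Φ(0.62/√(2/40) − 1.645) − 1 = 2Φ(1.128) − 1 = 0.741; with t tests, 73.0%.

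**4. Sensitivity to the assumptions.**
- Cut-off at month 21: 24 women short of week 12, and 61-67 short of the last visit.
- Cut-off at month 18: 36-37 and 78-83.
- Two recruitment years counted from month 4 (ending at month 28), cut-off at month 24: 28 and 63-67.
- All women entered by about month 21 (24 − 2.76 = 21.2), cut-off at month 24: none short of week 12.

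The week-12 count therefore moves freely with the assumptions. The 12-month count at a month-24 cut-off does not depend on how year-2 accrual is spread if the last visit is at 52 weeks: all 50 year-2 recruits then have under a year of follow-up. At 48 weeks, only those entered by about month 13 could have reached it.

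**5. Is early completion likely?** Table 6 needs 50 women in 8 to 9 months of year 1, or 50/9 = 5.6 to 50/8 = 6.3 per month. The recruitment rate cited from the group's other trials "averages about 4-5 participants/month". Slippage looks more likely than early filling.

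**6. When the data would be complete.** Last entry at month 24: week 12 at 24 + 2.76 = 26.8, about month 27; the last visit at 24 + 11.04 = 35.0, or 24 + 12 = 36.

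**The case against.** The strongest reply is that one loose sentence is being read as a data cut-off. It may mean only that analysis begins in year 2, or the year may simply be mis-stated. The rest of the plan points to complete follow-up: all women to 12 months, a model with three post-baseline times, and completers counted at 12 months. Table 6 also leaves out classes, scans and visits even for year 1, so the absence of a third-year row is weak evidence that work stops at month 24. Most of this stands. It makes the sentence the likely error, but it does not supply the missing date: nothing in the plan places follow-up or analysis after year 2.

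A reader might infer four stronger things that the documents do not support.

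- **That the study is underpowered by design.** The power statement rests on 90 completers and reproduces. No section plans an analysis on 80.
- **That the completer counts contradict the timeline.** They are dropout projections without calendar dates and conflict only once a month-24 cut-off is added.
- **That about 12 women will lack the primary visit.** That figure needs even accrual and a fixed cut-off. Memory training is given in groups of about 10, so entry may come in batches.
- **That the plan contains an unplanned interim look that biases later assessment.** Behavioral raters are blinded. Moreover, a properly timed primary analysis at month 27 would itself fall while women enrolled after about month 15 or 16 are still being followed: (24 − 16) × 4.17 ≈ 34 to (24 − 15) × 4.17 ≈ 38 of 100. Overlap with follow-up is therefore not in itself the fault.

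The mixed model's missing-at-random assumption is no full answer either. It tolerates missing visits but does not restore information from visits not yet made.

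**Conclusion.** The concern holds as a timeline inconsistency. Recruiting into the end of year 2, analysing in year 2 and following every woman for 12 months cannot all be done. If analysis closed at the end of year 2, 46 to 50 of 100 women would have no 12-month visit. The upper figure rests only on Table 6's 50 year-2 recruits and a 52-week last visit; the lower one also needs even accrual and a 48-week visit.

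The shortfall at week 12 (about 12 women, about 40 per group, power about 73-74% instead of 80%) is conditional on even accrual and a month-24 cut-off. It shows what a literal reading would cost and is not a defect in the sample size. The endpoint, model and randomisation are unaffected. The correction is small but should be made, because this is the plan's only statement of when the outcome data are analysed.

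**What to change.** Replace the year-2 sentence and extend Table 6 with follow-up and analysis rows tied to events, so that they move with recruitment:

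1. Primary analysis after the last randomised woman's week-12 visit and lock of the week-12 database (about month 27 on the present schedule).
2. The 6- and 12-month analyses after the last woman's final visit (about months 35-36). The 48-week and 52-week statements of that visit need to be reconciled.
3. No between-arm comparison of outcomes before the week-12 lock.
4. Outcome raters stay blinded, and are not shown between-arm results, until follow-up ends. This covers the roughly one third of women still in follow-up at the primary analysis.

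Table 6 should also say whether the two recruitment years run from the project start or from month 4. In the latter case recruitment ends at month 28, and the milestones move to about month 31 (28 + 2.76) and months 39-40 (28 + 11.04 to 28 + 12).

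The cost is wording and table rows, with no added participants or visits. The drawback is that, against the end of year 2, the primary result comes about 3 months later and the follow-up results 11-12 months later, and staff time has to be planned for that period.
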